7.8 Analysis of Secondary Endpoints

The secondary analysis endpoints are the PK parameters of *AGL* mRNA and ATX95, including T_{max} , C_{max} , AUC_{last} , AUC_{inf} , AUC_{tau} (RD Period only), R_{AUC} (RD Period only), T_{last} , $T_{1/2}$, CL , V_{ss} (SAD Period only). The secondary analyses will be analyzed for the PK Analysis Set and PP Analysis Set, if applicable.

Descriptive statistics will be summarized by number of subjects and arithmetic mean, SD, CV%, geometric mean, geometric SD, geometric CV%, median, minimum and maximum values for these PK parameters by analysis group in each applicable period, excluding total group in RD period. For T_{max} , only median, minimum and maximum values will be presented.

7.9 Analysis of Tertiary Endpoints

• [REDACTED]

7.9.1 Nutrition Diary data

Nutrition diary data such as daily caloric intake (total kcalories), daily protein intake (grams and % of total caloric intake), daily total carbohydrate intake (grams and % of total caloric intake), daily non-cornstarch carbohydrate intake (grams and % of total caloric intake), daily cornstarch intake (grams, grams/kg and % of total caloric intake), daily fat intake (grams % of total caloric intake), and daily sugar intake (grams) will be listed by cohort and visit. Weekly descriptive summaries for all the nutrition diary components will be provided.

At least 3 complete days out of 7 will be necessary for the calculation of mean weekly intakes. For each week, if more than 4 days are either missing or not checked as complete, the nutrition diary data is considered missing for that week.

The following sensitivity analysis may be considered:

- Exclude data from days marked complete and with total caloric intake less than 500 kcals and
- Include data from days not marked as complete and with total caloric intake within one standard deviation of the average of days completed.

All data, regardless of completeness status, will be included in the listings.

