^k If feasible, glycoNOE imaging of the liver, may be collected at the time of the liver MRI. Liver MRS are only required at sites with capability. Scanning for liver MRS can be conducted immediately following the liver MRI.

^l A 3- to 4-hour fasting period is preferred, but not required, prior to blood collection for serum HDL and LDL. All efforts should be made to obtain samples for HDL and LDL consistently for a given subject.

^m The nutrition diary recordings should be recorded at least 3 consecutive days per week through Screening and for the 3 consecutive days in the week leading up to each subsequent visit.

ⁿ The subject will receive CGM and HHG devices and will be trained on proper use at the Screening Visit. The CGM device is intended to be worn continuously from the Screening Visit to the EOS I D90/ET Visit. If the CGM device alarm notifies a subject that their blood sugar is abnormally high or low or the subject suspects their blood sugar is abnormally high or low, the subject will need to check their blood sugar with a HHG device that will be provided by Ultragenyx during screening. When CGM data is being collected, all subjects will connect their CGM and HHG devices to a study-provided laptop weekly and upload CGM and HHG data. At remote visits, in conjunction with assessments performed by a home health nurse, the site will contact subjects by telephone or videoconference to confirm the CGM device is properly in use and data was uploaded; answer any questions regarding or help troubleshoot (if necessary) CGM device use; and review CGM data, HHG data (when applicable), and nutrition diary entries; outside of scheduled visits, these telephone calls will occur as needed. At in-clinic visits, a conversation between the site and the subject should occur to ensure CGM compliance and troubleshoot if needed.

^o Serum and plasma samples will be collected for future biomarker assessments yet to be determined.

Note: White columns indicate in-clinic visits (Screening, BL D0, D1, and EOS I D90/ET). Gray columns indicate visits conducted at home by a home health nurse in conjunction with a phone call as needed (D4, D7, D14, D21, and D28).

Note: Laboratory assessments included in chemistry, hematology, and urinalysis are provided in [Appendix 3](#).

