10.4.4.4. Nutrition Diary

Subjects will be asked to maintain a record of daily diet using a diary at time points specified in [Table 4](#), [Table 5](#), and [Table 6](#). For all cohorts, the nutrition diary recordings should be recorded at least 3 consecutive days per week through screening or rescreening, as applicable, and for the 3 consecutive days in the week leading up to each subsequent visit. Qualified Investigator site staff should review nutrition diary data at each visit. Additional details regarding the nutrition diary are available in the Study Reference Manual.

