1 INTRODUCTION

The purpose of this Statistical Analysis Plan (SAP) is to provide details of the statistical analyses that have been outlined within the UX053-CL101 Protocol dated 3 January 2022. Changes from these guidelines must be substantiated by sound statistical reasoning and documented in the clinical study report (CSR).

Should there be a difference between the SAP and the protocol with respect to data analysis, the SAP will take precedence over the protocol.

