5 DEFINITIONS

5.1 Baseline

Baseline is defined as the last non-missing assessments prior to or on the date of initiation of the first dose of investigational product.

For nutrition diary data, baseline is defined as the average of all complete days (all values between screening and prior to dosing in SAD and between Stabilization Visit and prior to Dosing in RD). For CGM data, baseline is defined as the average of all daily measurements collected prior to the day of the first dose of IP administration.

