10.1.6 Missing Data for Other Efficacy Endpoints

When a change from baseline is assessed, missing data will not be imputed and only subjects with a baseline and at least 1 post-baseline measurement will be included in the analysis.

For the weekly nutrition diary data, at least 3 complete days out of 7 will be necessary for the calculation of mean weekly intakes. For each week, if more than 4 days are either missing or not checked as complete, the nutrition diary data is considered missing for that week.

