^d Assessments to be performed prior to dosing. The following assessments can be collected within a week prior to dosing, as long as there is 10 to 14 days between assessments that are repeated at the Screening Visit and the Baseline Visit: HHD, PROMIS questionnaires, SF-36v2, and GNEM-FAS expanded version.

^e Refer to Table 6 for the timing of vital sign assessments during dosing.

^f Refer to Table 7 for details of PK sampling. Please note that sample collections are marked for D1, D4, D7, D14, D21, and D28 in this table (Table 4) corresponding to a sample collection 1, 4, 7, 14, 21, and 28 days after infusion of UX053 on D0 as outlined in the final rows of the first column in Table 7.

^g Sample to be collected pre-dose and at the end of the infusion. Post-infusion blood samples should be collected in the opposite arm of the infusion to avoid dilution.

^h Close monitoring is required for subjects who develop elevations in ALT > 3x ULN and > 2x their baseline value, or elevation in ALT > 3x ULN with INR > 1.5. This includes repeating liver enzymes and INR within 48 hours and consideration of additional diagnostic tests such as liver ultrasound (Section 10.1.5).

ⁱ All efforts should be made for urine collections to be consistently taken from the first morning void.

^j Liver and calf MRS are only required at sites with capability. Scanning for liver and calf MRS can be conducted immediately following the liver MRI.

^k A 3 to 4 hour fasting period is preferred, but not required, prior to blood collection for serum HDL and LDL. All efforts should be made to obtain samples for HDL and LDL consistently for a given subject.

^l The nutrition diary recordings should be recorded daily from the Screening Visit through the EOS I D90/ET Visit.

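### A diary week needs three complete days of seven, but the current protocol requests only three before each visit, so one incomplete day suppresses that subject's weekly mean

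*SAP*

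**What the plan says.** SAP 7.9.1 plans weekly descriptive summaries of every diary component under the condition "At least 3 complete days out of 7 will be necessary for the calculation of mean weekly intakes". SAP 10.1.6 repeats the condition and gives its mirror image: "if more than 4 days are either missing or not checked as complete, the nutrition diary data is considered missing for that week".

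The SAP was written to the "UX053-CL101 Protocol dated 3 January 2022". Its SAD schedule (SAP 10.3, Table 4, footnote l) has a daily diary: "The nutrition diary recordings should be recorded daily from the Screening Visit through the EOS I D90/ET Visit".

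The current protocol asks for less. For the SAD cohorts (Synopsis, Table 4, footnote m) the post-screening diary is kept "for the 3 consecutive days in the week leading up to each subsequent visit". Section 10.4.4.4 says the same for all cohorts and, before dosing, asks for "at least 3 consecutive days per week through screening or rescreening, as applicable".

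Three other provisions bear on the effect:

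- SAP 5.1 does not apply the 3-of-7 rule to baseline: "For nutrition diary data, baseline is defined as the average of all complete days".
- SAP 7.9.1 lists every record whatever its completeness. It also mentions, as something that may be considered, a sensitivity analysis that adds back some days not marked complete.
- SAP 8 limits the analysis to SAD Cohorts 1S and 2S, with four subjects in each.

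**The concern.** The completeness threshold and the amount of data collected no longer belong together. Under a daily diary, three of seven is a lenient rule. Under a three-day request, the four days nobody asked for count towards the missing total, so the rule becomes a demand for perfect completion. SAP 1 gives the SAP precedence over the protocol on data analysis, so the protocol's newer schedule does not soften the rule.

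What is at stake is the descriptive summary of diet. Each cohort has at most four subjects, so one suppressed mean takes out at least a quarter of the values that could have entered a cohort's summary for that week. It does so because one day was incomplete, not because the other two were unusable.

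**Working it through.** **Inputs.** Threshold of 3 of 7 days (SAP 7.9.1, 10.1.6). Days requested: 7 of 7 in the SAP's schedule, 3 before each post-screening visit in the current protocol. SAD post-dose visits on Days 1, 4, 7, 14, 21, 28 and 90 (Protocol Table 4). Probability *p* that a requested day is marked complete: not in the documents, so assumed at 0.80, 0.90 and 0.95, with days independent.

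**1. The rule as written.** With *c* complete days, the week is missing when 7 − *c* > 4, that is, when *c* is 2 or less. It is usable when *c* is 3 or more. The two wordings agree for every *c* from 0 to 7.

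**2. Margin for loss.** Daily diary: 7 − 3 = 4 days. Three-day schedule: 3 − 3 = 0 days. With one requested day incomplete, *c* = 2, and 7 − 2 = 5 exceeds 4, so the week is missing.

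**3. Which SAD weeks are exposed.** Assume weeks counted from dosing (days 0–6, 7–13 and so on), visits on time, and diary days immediately before each visit.

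- Days 0–6 hold seven diary days: day 0 from the Day 1 run, days 1–3 from the Day 4 run and days 4–6 from the Day 7 run. This week has slack.
- The weeks feeding Days 14, 21, 28 and 90 hold exactly three days each (11–13, 18–20, 25–27 and 87–89) and have none.

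So four of the five post-dose weeks with diary days have no tolerance.

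**4. Probability that such a week is usable.**

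| Rule | Formula | *p* = 0.80 | 0.90 | 0.95 |
|---|---|---|---|---|
| 3 needed, 3 requested | *p*³ | 0.512 | 0.729 | 0.857 |
| 2 needed, 3 requested | *p*³ + 3*p*²(1 − *p*) | 0.896 | 0.972 | 0.993 |
| 3 needed, 7 requested | P(X ≥ 3), X ~ Bin(7, *p*) | 0.995 | 0.9998 | >0.9999 |

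**5. Per subject on the three-day schedule.** Expected suppressed weeks among the four exposed are 4(1 − *p*³) = 1.95, 1.08 and 0.57. Under two of three they are 0.42, 0.11 and 0.03.

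**6. Sensitivity to independence.** If incomplete days cluster, more runs are wholly complete at the same average *p*. In the extreme where a run is either all complete or all incomplete, both thresholds give *p* and the gain vanishes. The row for *p*³ is therefore the unfavourable end of the range.

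**The case against.** The rule matches the protocol it was written for, and a threshold equal to the number of days requested can be read as a test that the request was met. No figure in the documents supports a two-day mean. That stands: two against three is a judgement. But a rule that allows four missing days in seven was plainly not designed as an all-or-nothing test.

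Two stronger readings are tempting, and the documents support neither.

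*That the rule removes the check on dietary stability.* All diary records are listed by cohort and visit, and with eight subjects the listings serve that purpose well. Baseline averages all complete days. Dietary stabilisation is a requirement of the repeat-dose cohorts (Protocol 9.3), not of the SAD cohorts being analysed. The possible sensitivity analysis offers partial relief, but it is optional and cannot restore a day with no entry.

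*That a three-day run split across two weeks loses both weeks even at full compliance.* If weeks run from dosing, take a Day 14 visit within ±2 days and any of the five three-day runs in the seven days before it. Then 6 of 25 combinations (24%) straddle a boundary. The neighbouring week, however, is either week 1, normally filled by the Day 4 and Day 7 diaries, or week 3, normally filled by the Day 21 diary. With weeks on days 1–7, 8–14 and 15–21 and the visit counted as day 14, five of the six spill into week 1. At most week 2 would lose its mean, and the spilled days still count next door. The equal weighting of the 25 combinations has no basis in the documents. SAP 5.5–5.12, part of 7.9 and 10.2.1 are also blacked out, so it cannot be said that the SAP leaves the week undefined.

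It is also true that some subjects may have kept daily diaries. The protocol's summary of changes cites preliminary Cohort 1S data, so some follow-up predates the three-day schedule. For those records the rule keeps its four days of slack.

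**Conclusion.** The point holds in a limited form. For diary records collected under the current post-screening schedule, the 3-of-7 rule has no tolerance. One incomplete day suppresses that subject's mean in the weekly summary wherever no other visit's diary days fall in the same week. Between 51% and 86% of such weeks would be usable at assumed day-completeness of 0.80 to 0.95, against 90% to 99% if two of three days were enough.

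These percentages rest on an assumed completion rate and on independent days; clustering would narrow the gap. The list of exposed weeks assumes dosing-anchored weeks and on-time visits. The effect is confined to descriptive diary summaries: listings, the diary baseline, the primary safety analysis and the secondary PK analysis do not change. The number of subjects affected is at most eight and cannot be determined from the documents.

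**What to change.** In SAP 7.9.1 and 10.1.6, let the rule follow the schedule under which each record was collected.

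- **Three-day schedule:** summarise by visit. Average all complete post-dose days in the diary run belonging to that visit, require at least two, and display the number of days used. Exclude pre-dose days, which belong to baseline under SAP 5.1, and count no day for two visits. A plain seven-day look-back would break both conditions: from Day 4 it reaches before dosing, and the Day 4 and Day 7 windows overlap.
- **Daily diary:** keep the weekly summaries and the 3-of-7 rule. Moving these records to visit windows would drop most of the data between Day 28 and Day 90.
- State which schedule applied to each subject, and from what date.

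The cost is a few lines of SAP text and a small programming change. A two-day mean is noisier than a three-day mean: with independent days of equal variance its standard error is larger by √(3/2) ≈ 1.22. Showing the day count makes that visible.

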7.10 Analysis of Exploratory Endpoints

[REDACTED]

[REDACTED]

[REDACTED]

[REDACTED]

[REDACTED]

[REDACTED]

[REDACTED]

7.11 Analysis of Other Endpoints

7.11.1 Vital Signs

Descriptive statistics for vital signs (systolic and diastolic blood pressures, heart rate, respiration rate, temperature (C) and weight) and changes from baseline values at each visit and at the end of study will be presented by analysis group in each period. Individual subject listing and individual plots over time of vital signs parameters during dosing and separately over time for all visits will be provided.

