8.3.3. Study Stopping Criteria

Study enrollment and any further administration of study drug for subjects already enrolled, will be paused and the DMC and regulatory authorities will be notified if, at any time during the study, any of the criteria listed below occur after UX053 administration:

- Death of a subject
- Any serious TEAE with a severity \geq Grade 3 that is assessed as related to study drug or study procedures by the Investigator or Ultragenyx
- Any TEAE with a severity \geq Grade 3 affecting the cardiopulmonary, renal, or neurological systems, regardless of relationship to study drug, pending a DMC safety review

- Anaphylaxis, as defined by the National Institute of Allergy and Infectious Diseases/Food Allergy and Anaphylaxis Network (NIAID FAAN) criteria ([Table 11](#)), pending a DMC safety review
- Increases in ALT or AST $> 2x$ from Baseline and $> 3x$ the ULN, accompanied by total bilirubin $> 2x$ ULN or INR > 1.5 , without findings of cholestasis (defined as serum ALP activity $< 2x$ ULN) and in the absence of a plausible alternate explanation
- Increases in serum concentrations of ALT or AST $> 2x$ from Baseline and $> 3x$ ULN with the appearance of fatigue, nausea, vomiting, right upper quadrant pain or tenderness, fever, rash, or eosinophilia ($> 5\%$ of total leukocytes)
- 3 subjects develop platelet counts $< 50,000$ per mm³ (or thrombocytopenia \geq Grade 3 in severity)
- 3 subjects develop INR > 1.5 (or INR increase \geq Grade 2 in severity)

In addition to the above criteria, the DMC may at any time recommend dose reduction or discontinuation of dosing for an individual subject or for all subjects (Section [9.1.5](#)). Regulatory authorities will be notified immediately if the study stopping criteria are met and study enrollment or dosing is halted.

Table 11: Clinical Criteria for Diagnosing Anaphylaxis

Anaphylaxis is highly likely when any one of the following 3 criteria are fulfilled:

1. Acute onset of an illness (minutes to several hours) with involvement of the skin, mucosal tissue, or both (eg, generalized hives, pruritus or flushing, swollen lips-tongue-uvula)
 
AND AT LEAST ONE OF THE FOLLOWING
 
a. Respiratory compromise (eg, dyspnea, wheeze-bronchospasm, stridor, reduced PEF, hypoxemia) b. Reduced BP or associated symptoms of end-organ dysfunction (eg, hypotonia [collapse], syncope, incontinence)

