10.1.2. Vital Signs

Vital signs to be measured include seated systolic blood pressure and diastolic blood pressure, heart rate, respiration rate, temperature, and oxygen saturation. Vital signs are assessed at study visits specified provided in [Table 4](#), [Table 5](#), and [Table 6](#). The schedule of vital sign assessments during dosing visits is provided in [Table 7](#). Any new, clinically significant vital sign abnormalities should be captured as AEs.

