The severity or intensity of an AE refers to the extent to which an AE affects the patient's daily activities. The severity of all AEs will be graded using the Common Terminology Criteria for

Adverse Events (CTCAE) version 5.0, published on November 27, 2017, unless the AE is Cytokine Release Syndrome (CRS), in which case the AE will be graded by the American Society for Transplantation and Cellular Therapy (ASTCT) Consensus Grading for CRS (Lee et al., 2019).

Table 13: American Society for Transplantation and Cellular Therapy Consensus Grading for Cytokine Release Syndrome

CRS Parameter	Grade 1	Grade 2	Grade 3	Grade 4
Fever ^a	Temperature $\geq 38^{\circ}\text{C}$	Temperature $\geq 38^{\circ}\text{C}$	Temperature $\geq 38^{\circ}\text{C}$	Temperature $\geq 38^{\circ}\text{C}$
		with		
Hypotension	None	Not requiring vasopressors	Requiring a vasopressor with or without vasopressin	Requiring multiple vasopressors (excluding vasopressin)
		And/or ^b		
Hypoxia	None	Requiring low-flow nasal cannula ^c or blow-by	Requiring high-flow nasal cannula ^c , facemask, nonrebreather mask, or Venturi mask	Requiring positive pressure (eg, CPAP, BiPAP, intubation and mechanical ventilation)

^a Fever is defined as temperature $\geq 38^{\circ}\text{C}$ not attributable to any other cause. In patients who have CRS then receive antipyretic or anticytokine therapy such as tocilizumab or steroids, fever is no longer required to grade subsequent CRS severity. In this case, CRS grading is driven by hypotension and/or hypoxia.

^b CRS grade is determined by the more severe event: hypotension or hypoxia not attributable to any other cause. For example, a patient with temperature of 39.5°C , hypotension requiring 1 vasopressor, and hypoxia requiring low-flow nasal cannula is classified as grade 3 CRS.

^c Low-flow nasal cannula is defined as oxygen delivered at ≤ 6 L/minute. Low flow also includes blow-by oxygen delivery, sometimes used in pediatrics. High-flow nasal cannula is defined as oxygen delivered at > 6 L/minute.

Note: Organ toxicities associated with CRS may be graded according to CTCAE v5.0 but they do not influence CRS grading.

BiPAP, bilevel positive airway pressure; CPAP, Continuous positive airway pressure; CRS, cytokine release syndrome; CTCAE, Common Terminology Criteria for Adverse Events.

Source: (Lee et al., 2019).

If an AE cannot be graded using the CTCAE criteria, it should be graded using the following definitions:

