Section 8.3.3 Study Stopping Criteria	The following study stopping criterion was added: “3 subjects develop INR > 1.5 (or INR increase \geq Grade 2 in severity)”	To ensure subject safety per recommendation from regulatory authorities
Section 8.3.3 Study Stopping Criteria	The following text was added: “Regulatory authorities will be notified immediately if the study stopping criteria are met and study enrollment or dosing is halted.”	Updated per recommendation from regulatory authorities
Section 8.3.4 Subject Replacement and Section 11.1 Sample Size Determination	Text was added to indicate that subjects will not be replaced if they have received any study drug.	Updated per recommendation from regulatory authorities
Section 9.3 Nutrition Management and Section 9.7 Treatment Compliance	All instances of “Nutrition Guide” were changed to “Study Reference Manual.”	Nutritional guidance will be available in the Study Reference Manual.
Section 10.1.2 Vital Signs	Oxygen saturation was added to the list of vital sign assessments.	To ensure subject safety

Amendment 2.3 / 03 January 2022 / Substantial		
Section # and Name	Description of Change	Brief Rationale
Section 10.1.3 Electrocardiogram	RR was added to the list of measurements calculated for the electrocardiogram assessment.	To ensure subject safety
Section 0	In addition to glycogen content, muscle fat fraction in the calf will also be assessed during the calf ¹³ C Magnetic Resonance Spectroscopy (MRS) assessment.	Fatty degeneration of muscle should also be assessed, as it can affect the ¹³ C MRS signal for glycogen quantitation in muscle.
Section 10.5.6 AGL Gene Sequencing	Text was added to clarify that blood collected for AGL mutation analysis will be analyzed by a central laboratory.	To clarify the method of analysis
Appendix 1 Safety Definitions and Assessments	Text was added to define a TEAE.	Updated per recommendation from regulatory authorities
Appendix 1 Safety Definitions	Previously, the severity of all AEs were to be graded using the Common Terminology Criteria for Adverse Events (CTCAE) version 5.0, published on November 27, 2017. Text was added to reflect that the AE Cytokine Release Syndrome (CRS) will be graded by the American Society for Transplantation and Cellular Therapy (ASTCT) Consensus Grading for CRS (Lee et al., 2019). The grading scale is provided in Table 13.	Updated per recommendation from regulatory authorities

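### SAP 7.11.1 leaves oxygen saturation out of its closed list of vital signs to be summarised, although the protocol measures it and commits to summarising vital signs

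*SAP*

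**What the plan says.** Protocol 10.1.2 defines the vital signs as seated systolic and diastolic blood pressure, "heart rate, respiration rate, temperature, and oxygen saturation". Protocol Table 7 applies one measurement schedule to every infusion, and Protocol Table 4 adds vital signs at the later single-dose visits. Protocol 11.4 commits to summarising vital signs for all subjects and by treatment and cohort.

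SAP 7.11.1 names the vital signs as "systolic and diastolic blood pressures, heart rate, respiration rate, temperature (C) and weight" and asks for descriptive statistics and changes from baseline at each visit and at the end of study. Nothing marks the list as illustrative. A second sentence provides individual listings and individual plots of vital signs, during dosing and across visits, without repeating the list.

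On data analysis, SAP section 1 states that "the SAP will take precedence over the protocol". SAP section 8, on changes to the protocol's analyses, records only that the study stopped after 4 subjects in Cohort 1S and 4 in Cohort 2S, so that only those two cohorts are analysed.

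**The concern.** Safety is the primary objective of this first-in-human study, and hypersensitivity, including infusion-related reactions, heads the list of potential risks in Protocol 5.4.1. Two of the protocol's own tools for recognising and grading such reactions refer to low oxygen. The anaphylaxis criteria in Protocol Table 11 include "Respiratory compromise (eg, dyspnea, wheeze-bronchospasm, stridor, reduced PEF, hypoxemia"), and for cytokine release syndrome (CRS) Protocol Table 13 says "CRS grade is determined by the more severe event: hypotension or hypoxia not attributable to any other cause".

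Only new, clinically significant vital-sign abnormalities have to be recorded as adverse events. A modest shift in saturation below that threshold would therefore not reach the adverse-event tables, and under the SAP's list it would not reach the vital-sign tables either. A programmer who follows SAP 7.11.1 literally would produce mean and change-from-baseline tables for every protocol vital sign except this one. No reason is given.

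**Working it through.** The plan states no figure on this point, so there is none to reproduce. The check compares the texts and counts the values affected.

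1. **The two lists.**
   - Protocol 10.1.2: systolic pressure, diastolic pressure, heart rate, respiration rate, temperature, oxygen saturation (6 items).
   - SAP 7.11.1: systolic pressure, diastolic pressure, heart rate, respiration rate, temperature, weight (6 items).
   - In the protocol but not the SAP: oxygen saturation. In the SAP but not the protocol's list: weight.

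2. **Timing.** The SAP is written to the "UX053-CL101 Protocol dated 3 January 2022". The protocol's amendment history, among the Amendment 1 changes of 24 March 2021, records that "Oxygen saturation was added to the list of vital sign assessments", with subject safety as the reason. The item was therefore in force when the SAP was written. A lag between document versions does not explain the omission.

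3. **Which text governs.** Protocol 11.4 would cover saturation through the word vital signs. SAP 7.11.1 narrows that to its own list, and the SAP prevails. SAP section 8 does not declare the narrowing as a change.

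4. **Where saturation can still appear.** SAP 7.1 lists all raw case report form data. The second sentence of SAP 7.11.1 provides individual listings and plots. It can be read to include saturation, although the only definition of vital signs in that section leaves it out. No other visible SAP text mentions saturation.

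5. **Values missing from the by-visit table.**
   - Subjects: 4 + 4 = 8 (SAP section 8).
   - Visits in Protocol Table 4 after baseline: Days 1, 4, 7, 14, 21, 28 and 90 = 7.
   - Values: (1 baseline + 7 visits) x 8 = 64.
   - The schedule reproduced in the SAP also has Day 42. With it, (1 + 8) x 8 = 72.
   - Missed visits lower either count.

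6. **Infusion-day readings.** Protocol Table 7 schedules 1 pre-infusion reading, 3 in the first 45 minutes, 10 at hours 1 to 10, and 1 each at 16 and 24 hours: 1 + 3 + 10 + 1 + 1 = 16, excluding the optional discharge reading. For 8 subjects that is 16 x 8 = 128. SAP 7.11.1 tabulates by visit only, so for any vital sign at most one of the 16 readings per subject, the baseline, would enter the table under that visit.

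**The case against.** A reader might go further in three ways. The documents do not support them.

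- **That a fall in saturation during infusion is hidden because of this omission.** No vital sign has a planned within-infusion summary table. A fall in blood pressure at hour 2 would also be seen only in individual listings and plots. Adding saturation to the list does not by itself change that. For the same reason, it overstates the gap to count all 128 infusion-day readings plus 7 x 8 = 56 later ones, 184 in total. Most of them would not enter a table even if saturation were listed. The 24-hour reading and the Day 1 visit may also be the same measurement.
- **That saturation is the sign by which anaphylaxis is recognised and CRS graded.** In Table 11 hypoxemia is one example within respiratory compromise, alongside skin, blood pressure and gastrointestinal signs. In Table 13 hypoxia is one of three parameters, and its grade depends on the oxygen support required. Neither table uses a saturation cut-off.
- **That saturation is never reported.** Raw data are listed, the dosing plots may include it, and clinically significant abnormalities become adverse events. Protocol 11.4 also provides listings of abnormal vital signs. With 4 subjects per cohort, an individual plot shows a desaturation better than a cohort mean. Parts of the SAP, including the tertiary endpoint sections, are blacked out, so a mention there cannot be excluded.

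These points reduce the size of the problem. They leave the mismatch standing: SAP 7.11.1 itself is not blacked out, its list is closed, and it drops one protocol vital sign without explanation.

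**Conclusion.** The point holds. SAP 7.11.1 omits oxygen saturation, the only Protocol 10.1.2 vital sign left out. The omission runs against Protocol 11.4, and SAP section 8 does not declare it. The direct consequence is that about 64 scheduled values in 8 subjects have no by-visit or change-from-baseline summary (72 if Day 42 visits were held, fewer with missed visits).

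This rests on three assumptions: the list in SAP 7.11.1 is meant as written, no blacked-out section supplies the missing summary, and the subjects attended the scheduled visits.

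The weight is modest. The final analysis is descriptive, in 8 open-label single-dose subjects, and no estimate, test or error rate changes. It is still worth correcting, because the measurement is required, bears on the first-named risk, and belongs to a study whose primary objective is safety.

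**What to change.** Add oxygen saturation (%) to the parameter list in SAP 7.11.1, so that it enters the by-visit and change-from-baseline tables. State in the same section that the individual dosing-day listings and plots include it. If the omission was intended, declare it in SAP section 8 with the reason.

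As an option beyond the correction, report each subject's lowest saturation from the start of infusion to 24 hours and its change from the pre-infusion reading, by cohort. This would be a new derived row that the SAP specifies for no other vital sign, so it should be presented as an enhancement.

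The cost is one more parameter in existing table, listing and figure programs, plus one derived row if the option is taken. The protocol already requires the measurement, so no new data are needed.
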